7.1.6. SCD-Related Complications

7.1.6.1. Vaso-Occlusive Crisis (VOC)

VOC must be documented in the participant's medical record that the participant was seen by, or in contact with the Investigator or health care provider. The event may take place in a medical setting (hospital, clinic, emergency room) or at home.

Acute chest syndrome (ACS) is defined as an acute illness characterized by fever and/or respiratory symptoms, accompanied by a new pulmonary infiltrate on a chest X-ray.

VOC during the treatment period is defined as:

A composite of acute painful crisis or ACS, and includes the following:

- Moderate to severe pain lasting at least 2 hours
- No explanation other than VOC
- Requires oral or parenteral opioids, ketorolac, or other analgesics prescribed or directed by a healthcare professional
- May include episodes of ACS

VOC events and associated therapies will be summarized via descriptive statistics. These endpoints include:

- Rate of VOC during treatment with voxelotor
- Rate of VOC hospitalization during treatment with voxelotor
- Rate of RBC transfusion during treatment with voxelotor
- Rate of opioid use during treatment with voxelotor

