7.2.2.2. Diagnosis Versus Signs and Symptoms

If known, a diagnosis should be recorded on the CRF rather than individual signs and symptoms (eg, record only liver failure or hepatitis rather than jaundice, asterixis, and elevated transaminases). However, if a constellation of signs and/or symptoms cannot be

medically characterized as a single diagnosis or syndrome at the time of reporting, each individual event should be recorded separately on the CRF. If a diagnosis is subsequently established, it should be reported as follow-up information.

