7.2.2.5. Worsening of Sickle Cell Disease

Complications and symptoms of SCD should be recorded as an AE or SAE if judged by the Investigator to have worsened in severity and/or frequency or changed in nature during the study.

7.2.3. Serious Adverse Events, Serious Adverse Drug Reactions, and Requirements for Immediate Reporting

All SAEs, regardless of causal attribution, occurring on this study will be recorted on the AE eCRF and reported to Pfizer Safety via PSSA within 24 hours of the Investigator, designee, or site personnel's knowledge of the event. In the event that the EDC system is not available, paper SAE report forms will be used to report the SAE and faxed or emailed to Pfizer Safety.

The information reported on the paper SAE report form should be entered into PSSA once available.

The Sponsor may request additional information pertaining to the SAE from the investigational site. Follow-up reports must be submitted within 24 hours of awareness as additional information becomes available.

All SAEs regardless of causal attribution must be followed to resolution, stabilization or until reasonable attempts to determine resolution of the SAE are performed.

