# 2.1. Study Design

Study GBT440-034 is a multicenter, global, open-label extension (OLE) study available to participants who were previously enrolled and treated in Study GBT440-031. Participants must meet the entry criteria for this study to be eligible for enrollment.

All participants enrolled in GBT440-034, regardless of treatment received in the parent study GBT440-031 (i.e., placebo, voxelotor 900 mg, or voxelotor 1500 mg), receive treatment with voxelotor 1500 mg once daily (the highest dose deemed safe for continued assessment based on GBT440-031).

All participants in Study GBT440-034 have scheduled study visits with assessments at Day 1, Week 12, Week 24, and Week 48, and then every 24 weeks thereafter. Participants who were treated with placebo or voxelotor 900 mg in Study GBT440-031 have additional study visits with assessments at Week 4 and Week 8.

Participants may receive voxelotor in GBT440-034 as long as they continue to receive clinical benefit which outweighs risk as determined by the Investigator and/or until the participant has access to voxelotor from an alternative source (i.e., commercialization or through a managed access program).

Additional details and background information are provided in the study protocol.

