## **5.4. SCD-Related Complications**

## 5.4.1. Frequency of SCD-Related Complications

SCD-related complications include adverse events of acute chest syndrome, hepatic sequestration, leg ulcers, osteonecrosis, pneumonia, priapism, pulmonary hypertension, retinopathy, scleral icterus, sickle cell anaemia with crisis, splenic sequestration, and stroke.

The incidence and the annualized incidence rate of each SCD-related complication based on TEAEs, as well as the total of all SCD-related complications, will be computed. Annualized incidence rates will be estimated by dividing the total number of complications observed for all participants by the total assessment time for all participants, and 95% confidence intervals provided based on exact Poisson confidence limits.

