## **5.4.2.** Vaso-occlusive Crisis (VOCs)

Vaso-occlusive crises (VOCs) are as defined in protocol Section 7.1.6.1 and are a composite of acute painful crisis and acute chest syndrome events. The annualized incidence rate of ontreatment VOC events will be calculated and 95% confidence interval provided. VOC events with an onset date from informed consent to last dose date will be included in the summary.

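### Exact Poisson limits on the crisis and total complication rates (SAP 5.4.1) are too narrow if participants differ in underlying rate, and the VOC interval (SAP 5.4.2) names no method

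*SAP*

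**What the plan says.** SAP 5.4.1 estimates each annualized rate by "dividing the total number of complications observed for all participants by the total assessment time for all participants". It does this for twelve listed complications, among them sickle cell anaemia with crisis and acute chest syndrome, "as well as the total of all SCD-related complications, will be computed". The precision statement is "95% confidence intervals provided based on exact Poisson confidence limits". Neither document mentions overdispersion, robust variance, a bootstrap or any other participant-level term, and the SAP does not say what population rate the interval describes.

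For VOC, SAP 5.4.2 says: "The annualized incidence rate of ontreatment VOC events will be calculated and 95% confidence interval provided". No method is named.

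Four other places bear on the point:
- SAP 2.1 leaves treatment open-ended: "Participants may receive voxelotor in GBT440-034 as long as they continue to receive clinical benefit".
- Protocol 7.1.6.1 says of a VOC: "May include episodes of ACS".
- Protocol 7.2.2.2 says that "a diagnosis should be recorded on the CRF rather than individual signs and symptoms".
- Protocol 7.2.2.5 has SCD complications "recorded as an AE or SAE if judged by the Investigator to have worsened in severity and/or frequency" or to have changed in nature.

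**The concern.** A crisis can recur many times in one participant. Pooling the counts and applying Poisson limits treats every event as independent and every participant as having the same rate. SAP 5.2 summarises genotype, hydroxyurea use and region as baseline characteristics. Differences in crisis rate across such a population are plausible, although the documents report no rates. Open-ended follow-up does not create the extra variation, but it amplifies it.

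The total has a second problem. Acute chest syndrome and sickle cell anaemia with crisis are listed separately, so one episode could add two counts. That inflates the variance even when all participants share one rate.

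SAP 5.4.1 and 5.4.2 contain the only confidence intervals in the SAP. In a study without tests (SAP 5) they are the stated precision of the long-term crisis, total and VOC rates. Under SAP 4.2 they are shown overall and, as appropriate, by prior treatment group.

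**Working it through.** **Inputs from the documents.** Confidence level 95%, pooled estimator and exact Poisson limits (SAP 5.4.1); at most 274 participants (SAP 2.3).

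**Assumed inputs.** Annual rate r = 0.3, 1 or 3. Relative variance of participant rates v = 0.5, 1 or 2 (gamma-distributed). Follow-up t = 2 years each. About 90 participants in one prior-treatment group.

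**Reproducing the plan's figure.** With v = 0 the simulated exact interval covers about 95%, as stated.

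**Heterogeneity.** A participant's count has mean rt and variance rt + v(rt)². The variance of the pooled count is therefore inflated by

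V = 1 + v·r·t, here 1 + 2vr,

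whatever the number of participants. Approximate coverage is 2Φ(1.96/√V) − 1. For r = 1 and v = 1, V = 3, 1.96/√3 = 1.13, and coverage is 74%.

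| Rate per year | V for v = 0.5 / 1 / 2 | Formula coverage | Simulated, N = 274 | Simulated, N = 90 |
|---|---|---|---|---|
| 0.3 | 1.3 / 1.6 / 2.2 | 91 / 88 / 81% | 92 / 88 / 82% | 92 / 89 / 84% |
| 1 | 2 / 3 / 5 | 83 / 74 / 62% | 84 / 74 / 63% | 85 / 76 / 63% |
| 3 | 4 / 7 / 13 | 67 / 54 / 41% | 67 / 54 / 42% | 68 / 55 / 42% |

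(20,000 simulations per scenario; repeat runs agree within one to two points.)

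**Threshold.** Coverage is 90% when 1.96/√V = 1.645, so V = 1.42 and vr = 0.42/2 = 0.21.

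**Milder heterogeneity.** Two equal groups whose rates differ k-fold have v = ((k − 1)/(k + 1))², which is 0.11/0.25/0.44 for k = 2/3/5. Simulated coverage is 95/94/92% at 0.3 per year, 92/89/85% at 1 and 87/79/70% at 3.

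**Low rate.** At 0.1 per year with gamma v = 0.5/1/2, coverage is 95/94/91%.

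**Unequal follow-up.** With follow-up uniform on 0.5 to 4.5 years and v = 0.5/1/2, coverage is 90/84/75% at 0.3 per year, 80/68/55% at 1 and 59/47/37% at 3. With a common rate it stays at 95%.

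**Other target.** Against the realised average rate of the enrolled cohort, the exact interval covers 95–96% in all the gamma scenarios of the table.

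**Linked events in the total, no heterogeneity.** If each episode adds a second count with probability p, the inflation is (1 + 3p)/(1 + p). For p = 0.1/0.2/0.3/0.5 this is 1.18/1.33/1.46/1.67, and formula coverage is 93/91/90/87%. Simulation agrees, and the result is the same under either target.

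**Participant-level limits.** A log-scale interval with participant-clustered sandwich variance covers about 95% in the heterogeneity and linked-event scenarios. Its width relative to exact Poisson is about √V: 1.1/1.3/1.5 at 0.3 per year, 1.4/1.7/2.2 at 1 and 2.0/2.6/3.6 at 3. In one simulated dataset the model returned exactly total events over total time (1.063 per year), with limits 0.92–1.23 against 0.99–1.14 for exact Poisson.

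**Sparse counts.** At 0.005 per year, N = 90 and 2 years, 0.9 events are expected. No events occur in e^(−0.9) = 41% of samples, where the sandwich is undefined. Otherwise it covers about 90%, against 98–99% for exact Poisson.

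**The case against.** The arithmetic is not in dispute. The case against rests on target, size and consequence.

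- **Target.** The SAP does not say its intervals describe patients like those enrolled. If only the cohort's realised average is meant, exact Poisson is valid for a single event type, and participant-level limits are conservative (97–100% coverage at 0.3–3 per year with v = 0.5–2). This stands. The remedy is to state the target; the wider population is the usual reading of an interval for a long-term event rate.
- **Size.** No rate or dispersion is given, and Protocol 7.2.2.5 may lower the crisis counts taken from adverse events. At 0.1 per year, or with two groups differing two- or threefold at 0.3 per year, the shortfall is four points or less. This stands: the low coverage at 3 per year is conditional on the assumptions.
- **Double counting.** Protocol 7.1.6.1 defines the VOC endpoint, not adverse event coding, and Protocol 7.2.2.2 could reduce paired entries. The linkage frequency is unknown, and 10–20% linkage costs only two to four points.
- **VOC.** That 5.4.2 would use the 5.4.1 limits is an inference. The table mock-ups, which are a separate document, might name a method.
- **Consequence.** Analyses are descriptive. Protocol 8.1.1.2 foresees comparison with GBT440-031, but SAP 5.4.1 does not repeat it, and the SAP supersedes the protocol where they differ.

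None of this makes the limits right for a recurrent event in a mixed population. Being descriptive limits the harm, but an interval labelled 95% should still say what it covers.

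**Conclusion.** The concern holds. Given any between-participant difference in rate, with Poisson counts within a participant, exact Poisson limits are too narrow for the rate in patients like those enrolled, and more participants do not cure it. For the total, linked events would add a shortfall under either target.

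The size depends on assumed rates, dispersion and follow-up. It runs from negligible at about 0.1 per year to coverage of 42–67% at 3 per year with gamma variance 0.5–2. With 2 years each, coverage falls below 90% once variance times annual rate exceeds about 0.21. Point estimates are unaffected and no decision uses the intervals. The harm is overstated precision for the crisis and total rates, and for the VOC rate if it takes the same limits. It should be corrected because the correction is cheap.

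**What to change.** Keep the point estimate. In SAP 5.4.1, add text to this effect:

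*For sickle cell anaemia with crisis and for the total of all SCD-related complications, the 95% limits describe the rate in patients like those enrolled. They come from a Poisson model with a log assessment-time offset and participant-clustered sandwich variance.*

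A participant bootstrap is an acceptable alternative. Clustering by participant also covers linked events. Keep exact Poisson for the other eleven listed complications, named in advance, with the footnote *these limits assume no extra-Poisson variation*. Some of these may also recur, so the footnote should not call them rare. In SAP 5.4.2, state that the VOC interval uses the participant-level method.

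The cost is two sentences and a footnote in 5.4.1, one sentence in 5.4.2 and a standard model call. The downsides are wider intervals for crisis, total and VOC, and two interval methods in one table. The sandwich should not be extended to every complication, because it fails with sparse counts. If the sponsor wants only the realised cohort average, the SAP should say so; the participant-level limits would then be conservative for it.

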## **5.4.2.** Vaso-occlusive Crisis (VOCs)

Vaso-occlusive crises (VOCs) are as defined in protocol Section 7.1.6.1 and are a composite of acute painful crisis and acute chest syndrome events. The annualized incidence rate of ontreatment VOC events will be calculated and 95% confidence interval provided. VOC events with an onset date from informed consent to last dose date will be included in the summary.

#### 5.4.3. Therapies Associated with Sickle Cell Disease

The incidence rate and reasons for on-treatment red blood cell (RBC) transfusions will be summarized. RBC transfusions with an onset date from informed consent to last dose date will be included in the summary.

Opioid usage will be identified based on reported concomitant medications. The number and percentage of participants reporting opioid use at baseline and post-baseline will be summarized.

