8.1.1.2. Frequency of SCD-Related Complications

Over the course of the treatment period, the frequency of SCD complications for each participant will be recorded. SCD complications may include the following: VOC, acute chest syndrome, hepatic sequestration, leg ulcers, priapism, pulmonary hypertension, retinopathy, scleral icterus, splenic sequestration, and stroke. The incidence and rate of each complication and the totality of all SCD-related complications will be computed and then compared to those observed in the GBT440-031 study.

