8.1.1.2.1. Therapies Associated with VOC

During the treatment period, RBC transfusion and opioid usage will be recorded. The incidence and rate of these therapies will be calculated and compared to those observed in the GBT440-031 study.

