#### 2. INTRODUCTION

The objective of Study GBT440-034 (C5341022) is to assess the long-term safety and treatment effect of voxelotor in participants with sickle cell disease (SCD) who have completed treatment in Study GBT440-031.

This statistical analysis plan (SAP) provides details of the planned analyses and statistical methods for Study GBT440-034 final clinical study report (CSR). Where this document differs from the high-level analysis plan described in the study protocol, the methodology described in this SAP is considered the latest and supersedes the corresponding section(s) in the protocol.

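### SAP 5.4.3 replaces the protocol's rate of opioid use with percentages at baseline and post-baseline, with no time window, no person-time and no stated reason

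*SAP*

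**What the plan says.** Protocol 7.1.6.1 includes, in its list of VOC and therapy endpoints, "Rate of opioid use during treatment with voxelotor". The same list has rates of VOC, VOC hospitalization and RBC transfusion. Protocol 8.1.1.2.1, on transfusion and opioid usage, says "The incidence and rate of these therapies will be calculated and compared to those observed in the GBT440-031 study". The synopsis says the same.

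SAP 5.4.3 treats the two therapies differently. Transfusions get an incidence rate and a window: "RBC transfusions with an onset date from informed consent to last dose date will be included in the summary". Opioid use is taken from concomitant-medication records, and the whole plan for it is "The number and percentage of participants reporting opioid use at baseline and post-baseline will be summarized". SAP 5.4.2 gives VOCs an annualized rate with the same window, and SAP 5.4.1 obtains complication rates by "dividing the total number of complications observed for all participants by the total assessment time for all participants". No other SAP section supplies an opioid rate.

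SAP 2 says that, where the two documents differ, "the methodology described in this SAP is considered the latest and supersedes the corresponding section(s) in the protocol".

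**The concern.** A measure named in the protocol disappears without explanation, and its replacement is not fully defined. SAP 3.1 defines a baseline value in terms suited to laboratory records. It does not say when a medication counts as in use at baseline, nor whether post-baseline opioid use means any use, use per visit or use per year, nor when counting stops. The end point matters: Protocol 5.5.1 records concomitant medications until 28 days after the last dose, whereas the SAP closes its VOC and transfusion windows at the last dose.

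If post-baseline means any use, the percentage depends on how long each participant is followed. Treatment has no fixed end (SAP 2.1), and the analysis windows run to Week 192 and continue (SAP 3.2, Table 1). A table showing baseline beside post-baseline invites a before-and-after reading. On this definition, opioid use could seem to increase on voxelotor when only the observation time has grown.

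**Working it through.** **1. Protocol against SAP.**

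| Item in Protocol 7.1.6.1 | In SAP 5.4? |
|---|---|
| VOC rate | Yes, annualized, consent to last dose (5.4.2) |
| VOC-hospitalization rate | No |
| RBC transfusion rate | Yes, consent to last dose (5.4.3) |
| Opioid-use rate | No; percentages only, no window (5.4.3) |

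The percentage can serve as the incidence that Protocol 8.1.1.2.1 asks for. The rate is lost. The comparison with GBT440-031, promised for these therapies and also for complications (Protocol 8.1.1.2: "will be computed and then compared to those observed in the GBT440-031 study"), appears nowhere in SAP 5.4.

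**2. Direction on the any-use reading.** Once a participant has used an opioid after baseline, further follow-up cannot undo it. The cumulative percentage in a fixed set of participants therefore cannot fall as follow-up lengthens. This needs no assumed rate.

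**3. Size, for illustration only.** The documents give no opioid figure, so there is nothing to reproduce, and both inputs below are assumptions. Let a fraction b use opioids continuously and let the others start at a constant rate λ per person-year, so that underlying use does not change. Then

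any use by time T = b + (1 − b)(1 − exp(−λT)).

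The target days come from SAP Table 1: T = 336/365.25 = 0.920 years (Week 48), 504/365.25 = 1.380 (Week 72, the parent-study maximum in Protocol Table 1) and 1344/365.25 = 3.680 (Week 192).

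| λ | b | Week 48 | Week 72 | Week 192 |
|---|---|---|---|---|
| 0.1 | 20% | 27.0% | 30.3% | 44.6% |
| 0.1 | 80% | 81.8% | 82.6% | 86.2% |
| 0.25 | 50% | 60.3% | 64.6% | 80.1% |
| 0.5 | 20% | 49.5% | 59.9% | 87.3% |
| 0.5 | 80% | 87.4% | 90.0% | 96.8% |

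For λ = 0.5 and b = 20%, Week 192 is 0.2 + 0.8 × (1 − exp(−1.840)) = 87.3%. Over λ from 0.1 to 0.5 and b from 20% to 80%, follow-up alone adds between 86.2 − 81.8 = 4.4 and 87.3 − 49.5 = 37.8 points from Week 48 to Week 192. From Week 72 to Week 192 it adds between 86.2 − 82.6 = 3.6 and 87.3 − 59.9 = 27.4 points. The effect shrinks as continuous use rises.

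**4. Checking the candidate remedies in the same model.**

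- *Percentage per 24-week interval*, T = 168/365.25 = 0.460 years. It does not grow with follow-up, but that follows from the constant-rate assumption. For b = 20% it is 23.6% at λ = 0.1 and 36.4% at λ = 0.5; for b = 80% it is 80.9% and 84.1%. Against a single-day baseline (about b, if courses are short) it is too high by 80.9 − 80 = 0.9 to 36.4 − 20 = 16.4 points with no change in use. A fair comparison needs a baseline look-back of the same length.
- *New courses per person-year.* Continuous users add person-time but no new starts, so the expected value is (1 − b)λ. At λ = 0.5 this is 0.8 × 0.5 = 0.40 for b = 20%, but 0.2 × 0.5 = 0.10 for b = 80%. More continuous use gives a lower figure, so this measure cannot stand alone.

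**The case against.** The protocol leaves analysis detail to the SAP, and the SAP says that it prevails, so there is no dispute about which text applies. Every analysis is descriptive (Protocol 8.3, SAP 5), so no error rate or test is affected. Opioid use is not named in the main endpoint sections of either document. For a chronic medication, a percentage of users is a defensible summary. All of this stands, and it limits the severity. It does not explain why a listed measure was dropped, and it does not define the one that remains.

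A reader might infer that the opioid percentage will be inflated by a known amount. The documents do not support that. The table mock-ups are in a separate document (SAP 6) and may define post-baseline. The SAP summarizes laboratory values and vital signs at each evaluation after baseline, so an interval display is not excluded. The inputs in the illustration are assumed. Protocol 5.5.2 names codeine among commonly taken chronic medications, so the effect may be small.

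A reader might also infer that follow-up differs between prior-treatment groups. No section shows this, and SAP 5.2 tabulates time on study, which would reveal unequal follow-up without standardizing the opioid figure for it.

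Nor are opioids the only omission, since the VOC-hospitalization rate is dropped in the same way.

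**Conclusion.** The omission is certain from the text: SAP 5.4.3 drops the opioid rate, gives no reason, and leaves a percentage with no window or person-time. The follow-up problem is conditional. It arises if post-baseline means any use, in which case the direction is certain and the size is unknown. The 3.6 to 27.4 points from Week 72 to Week 192 rest on assumed values of b and λ, a constant starting rate and follow-up of all participants to Week 192.

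On that reading, the figure cannot be interpreted against baseline or against GBT440-031. The severity is minor to moderate, because the study is descriptive and the loss is one of interpretability. The missing VOC-hospitalization rate and the missing GBT440-031 comparison are separate gaps in SAP 5.4 and do not make the opioid point more serious.

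**What to change.** In SAP 5.4.3:

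- Keep the percentages, and define baseline use and post-baseline use.
- Add a time-standardized summary limited to first dose through last dose, which fits the protocol's during-treatment wording. If the SAP's consent-to-last-dose convention is preferred, state it as such, since it can start before treatment.
- As the preferred summary, report the percentage of participants using opioids in consecutive 24-week intervals, among those under observation. State a rule for partly observed intervals, and use a baseline look-back of equal length. If the look-back reaches into GBT440-031, label it by prior treatment (placebo, 900 mg, 1500 mg), because it is not a common untreated baseline.
- If a rate is reported, use one that counts continuous users, such as opioid-use days per person-year, or give new courses per person-year beside the percentage of continuous users. New courses alone should not be presented as the protocol's rate, which the protocol does not define.

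Separately, restore the VOC-hospitalization rate in SAP 5.4.2 or explain its removal. For SAP 5.4 as a whole, show the GBT440-031 comparison or say why it was dropped.

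For opioids, the cost is SAP wording and one or two table rows. Protocol 5.5.1 already requires medication, dose, duration and indication. The drawbacks are that as-needed use may be poorly dated, and that any look-back or comparison depends on parent-study records not described in these documents.
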